2.3 Participant disposition, demographics and other baseline characteristics

The FAS will be used for all participant demographic and baseline characteristic summaries and listings unless otherwise specified. For continuous data, mean, standard deviation, median, minimum, and maximum will be presented.

2.3.1 Enrollment status

The number and percentage of participants enrolled will be summarized by country, site, and cohort.

In addition, the number of participants screened will be summarized by country and site. For subjects who are screen failures, the reasons for not completing screening will be summarized based on the “Disposition” eCRF.

2.3.2 Basic demographic and background data

Demographic and other baseline data including disease characteristics will be listed and summarized descriptively by cohort. Categorical data will be presented as frequencies and percentages.

Body mass index [kg/m²] will be calculated as weight [kg] / (height [m]²) using weight and height at baseline.

2.3.3 Diagnosis and extent of cancer

Summary statistics will be tabulated for diagnosis and extent of cancer. This analysis will include primary site of cancer, tumor histology, time (in months) since initial diagnosis, stage at initial diagnosis, time (in months) from initial diagnosis to first recurrence/progression, time (in months) since most recent relapse/progression, stage at time of study entry, number and type of metastatic sites, as well as disease burden (sum of target lesion diameters at baseline, based on BIRC and investigator assessment). Metastatic sites will be based on the “Diagnosis and Extent of Cancer” eCRF. Data on diagnosis and extent of cancer will also be listed.

2.3.4 Biomarker status

The biomarker test type (central versus local) and sample type (tissue versus blood) used for status determination for eligibility will be summarized per biomarker. A summary of the biomarker status (mutation or expression level) between local (based on tumor or plasma) and central testing (based on tumor) will be provided. Details of the biomarker testing and results will be listed.

When multiple testing types and sample types are available, the biomarker status in the geographic table follows:

1. If both tumor and plasma samples are available, testing results based on the tumor will be used.

2. If both local and central testing are available, the patient will be considered a mutant if either local or central testing is positive.in

2.3.5 Medical history

Relevant medical histories and current medical conditions at baseline will be summarized and listed. The summaries will be presented by primary system organ class (SOC) and preferred term (PT). Medical history and current medical conditions will be coded using the Medical Dictionary for Regulatory Activities (MedDRA) terminology. The MedDRA version used for reporting will be specified in the CSR and as a footnote in the applicable tables/listings.

2.3.6 Analysis sets

The number and percentage of participants in each analysis set will be summarized. Reasons for exclusion of participants from analysis sets will be tabulated.

2.3.7 Screening phase disposition

Screen failures recorded in the screening phase disposition will comprise participants who signed the molecular pre-screening ICF and were screen failed or were screened but were not enrolled into the study. Frequency counts and percentages will be tabulated for all enrolled participants as follows:

- Number (%) of participants ongoing in the screening phase.
- Number (%) of participants who completed the screening phase
- Number (%) of participants who discontinued during the screening phase (participants did not continue into the next phase of the study)
- Reasons for screening phase discontinuation

All screen failure participants with reasons for screen failure will be listed.

2.3.8 Participant disposition

For the participant disposition summary table, the following information (and potentially additional subcategories) will be presented:

Participants enrolled:

- Number (%) of participants treated
- Number (%) of participants not treated

Related to the on-treatment period:

- Number (%) of participants who are still on-treatment
- Number (%) of participants who discontinued treatment and continued in the follow-up period
 - Primary reasons for study treatment discontinuation
- Number (%) of participants who discontinued the study

Related to the post-treatment period:

- Number (%) of participants who are still in the follow-up period
- Number (%) of participants who discontinued from the post-treatment follow-up period
 - Primary reasons for discontinuation from the post-treatment follow-up period

The information will be derived from the applicable “Subject status” and “Disposition” eCRFs. The disposition information will also be listed.

2.4 Protocol deviations

The number and percentage of participants in the FAS with any protocol deviation will be tabulated by deviation category (as specified in the edit checks specification document). All protocol deviations will be listed.

In addition to the pre-defined standard PD terms, Novartis has defined 6 new protocol deviations and the corresponding relationship (health status related, site lockdown, patient concerns, drug supply issue etc.) to the COVID-19 pandemic in line with “FDA Guidance on Conduct of Clinical Trials of Medical Products during COVID-19 Public Health Emergency” (Food and Drug Administration 2021) and “Guidance on the management of clinical trials during the COVID-19 (coronavirus) pandemic” ([European Medicines Agency 2022](#)). The following deviations related to the COVID-19 pandemic will be summarized.

- Missing visits
- Changes in procedures and assessments
- Planned visits not done at sites
- Changes in drug supply method
- Treatment not given
- Participant discontinuation due to COVID-19 situation

A cross-tabulation of COVID-19 related PD vs. relationship will also be produced. In addition, COVID-19 related outcomes (e.g., COVID-19 AEs, discontinuation due to COVID-19, death due to COVID-19) will be descriptively summarized by country, sites, and cohort.

2.5 Treatments (study treatment, rescue medication, concomitant therapies, compliance)

The safety set will be used for all medication data summaries and listings unless otherwise specified.

2.5.1 Study treatment / compliance

Duration of exposure to study treatment, cumulative dose, dose intensity (DI), and relative dose intensity (RDI) will be summarized for the on-treatment period. The duration of exposure will be categorized into time intervals (< 6, ≥ 6 –< 12, ≥ 12 –< 24, ≥ 24 –< 48, ≥ 48 weeks); frequency counts and percentages will be presented for the number of participants in each interval. A categorical summary of the RDI will be presented ($\leq 75\%$, $> 75\%–\leq 90\%$, $> 90\%–\leq 110\%$, $> 110\%$).

The number (%) of participants who have dose reductions, interruptions, and the respective reasons, and the number (%) of participants who have dose escalation for one dose level after dose reduction will be summarized in the on-treatment period.

Participant level listings of all doses administered on treatment along with dose change reasons will be generated. A listing of participants receiving study drug from specific batches (for CSR appendix 16.1.6) will also be generated.

2.5.1.1 Duration of exposure

Duration of exposure to study treatment is defined as:

- Duration of exposure to study treatment (days) = (last date of exposure to study treatment) – (date of first administration of study treatment) + 1;
- Duration of exposure to study treatment (weeks) = (duration of exposure to study treatment)/7.

The last date of exposure to study treatment is defined in [Section 2.1.3.4](#). The duration includes periods of temporary interruption.

2.5.1.2 Cumulative dose

Cumulative dose is defined as the total dose given during the study treatment exposure and will be summarized for each cohort. For participants who did not take any study treatment the cumulative dose is by definition equal to zero.

The cumulative dose is calculated using the information from the “Study Treatment” eCRF and is expressed in mg. The cumulative dose is the sum of the non-zero doses recorded over the dosing period.

2.5.1.3 Dose intensity and relative dose intensity

Dose intensity (DI) is defined for participants with non-zero duration of exposure as follows:

- DI (mg/day) = cumulative dose (mg) / duration of exposure to study treatment (day).

For participants who did not take any drug the DI is by definition equal to zero.

Planned dose intensity (PDI) is the assigned dose by unit of time planned to be given to participants as per protocol in the same dose unit and unit of time as for dose intensity. Planned dose intensity is 400 mg/day (200 mg b.i.d.).

Relative dose intensity (RDI) is defined as follows:

- RDI (%) = [DI (mg/day) / PDI (mg/day)] × 100

2.5.1.4 Dose reductions, interruptions, or escalations

The number and percentage of participants who had dose reductions or interruptions with the corresponding reasons and the number and percentage of participants who had a dose escalation of one dose level after a dose reduction will be summarized. Permanent discontinuations of study treatment will be summarized in the disposition table.

The duration of the dose interruption will be summarized by time intervals in weeks for each observed interruption (< 1 week, 1–2 weeks, 2–3 weeks, ...) as well as by descriptive statistics. The time intervals may be adjusted depending on the observed data. The duration of a dose interruption is defined as (start date of the first dose administration after interruption – start date of the dose interruption).

The “Dose interrupted” and “Dose change” option from the type of change field of the “Study Treatment” eCRF will be used to determine the dose interruptions and dose changes (reductions, escalations) respectively. The corresponding fields “Reasons for dose change” from the “Study Treatment” eCRF will be used to summarize the reasons.

Interruption: An interruption is defined as a dose of zero given on one or more days between two non-zero dosing records.

For the purpose of summarizing interruptions and reasons, any two or more consecutive zero doses will be counted as one interruption if the reasons for these two consecutive dose interruptions are the same. They will be counted as two different interruptions only if the reasons are different. If an interruption occurs for more than one day due to the same reason, but the days are not consecutive, i.e., there is at least one dosing day in between, then each dose interruption will be counted as a different occurrence. For participants who have dose interruption checked on the eCRF but never resume a non-zero dose, the dose interruption will not be counted.

Dose reduction: A dose reduction is defined as a decrease of the total daily dose from the protocol planned starting dose (200 mg b.i.d.) to another non-zero dose or a decrease from the previous dose that is less than the protocol planned starting dose to another non-zero dose, even if the decrease has been directly preceded by an interruption.

The number of dose reductions will be derived programmatically based on the change and the direction of the change.

- If a participant received less than the protocol planned dose (nonzero) for one day without any reason, then this is not a dose reduction. This applies to the first dosing record.
- If, due to a dosing error, a participant receives higher than protocol planned dose and moves down to the planned dose then this is not a dose reduction. However if the change is directly from a higher than planned dose down to a lower than protocol planned dose, then this is a dose reduction.
- If due to interruption, a participant receives less than the previous total daily dose for 1 day and **followed** by an interruption (due to the same reason) then this is NOT a dose reduction. If due to interruption, a participant receives less than previous total daily dose for 1 day **after** an interruption (due to the same reason) then this is NOT a dose reduction. After interruption, dose reduction will be determined using the dose received on a day not related to interruption.
- If a patient receives half of the dose **on the last day** of treatment (for ex: 200 mg BID from 30-May-2023 to 03-Oct-2023, and 200 mg QD on 04-Oct-2023), then this is

NOT a dose reduction. This rule is applied for any dose levels (for ex: 100 mg BID from 15-Dec-2023 to 20-Dec-2023, and 100 mg QD on 21-Dec-2023).

For examples of dose change, refer to the eCRF completion guidance document.

Dose escalation: A dose escalation is defined as an increase to the next higher dose level after the participant had a dose reduction. According to study protocol section 6.5.1 a participant is only allowed to have one such escalation.

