If the participant requires a dose interruption of more than 21 days from the intended day of the next scheduled dose, then the participant must be discontinued from the study treatment. Exceptions to this criterion may be considered if the participant is deriving clinical benefit from the treatment. The Investigator must discuss and receive approval from Novartis Global Medical Director or designee prior to continuing study treatment in this situation and rationale should be captured in the source documents. If study treatment is reintroduced after an interruption of more than 21 days caused by an adverse event, study treatment can only be reintroduced at a lower dose level. If study treatment is reintroduced after an interruption of more than 21 days that was not caused by an adverse event, study treatment may be reintroduced without dose reduction.

All dose changes must be recorded on the appropriate eCRF.

Criteria for dose reduction / interruption and re-initiation of JDQ443 treatment for adverse drug reactions. Table 6-3

	reactions.
Dose modifications for JDQ443	
Worst toxicity	
CTCAE Grade ^a (value) during a cycle of therapy	
Investigations (Hematologic)	
Neutropenia (ANC)	
Grade 1 (ANC < lower limit of normal (LLN) - 1500/mm³)	Recommendation: Maintain study treatment and dose level.
Grade 2 (ANC < 1500 - 1000/mm ³)	Recommendation: Maintain study treatment and dose level.
Grade 3 (ANC < 1000 - 500/mm ³)	Recommendation: Interrupt study treatment until resolved to ≤ Grade 2, then:
	If resolved in ≤ 7 days, maintain dose level.
	If resolved in > 7 days, reduce 1 dose level.
Grade 4 (ANC < 500/mm³)	Mandatory: Interrupt study treatment until resolved to ≤ Grade 2, then reduce 1 dose level.
Thrombocytopenia	
Grade 1 (PLT < LLN - 75,000/mm ³)	Recommendation: Maintain study treatment and dose level.
Grade 2 (PLT < 75,000 - 50,000/mm ³)	Recommendation: Maintain study treatment and dose level.
Grade 3 (PLT < 50,000 - 25,000/mm ³)	Recommendation: Interrupt study treatment until resolved to ≤ Grade 2, then:
	If resolved in ≤ 7 days, maintain dose level.
	If resolved in > 7 days, reduce 1 dose level.
	Mandatory: For Grade 3 thrombocytopenia associated with major bleeding, permanently discontinue study treatment.
Grade 4 (PLT < 25,000/mm³)	Mandatory: Interrupt study treatment until resolved to ≤ Grade 2, then reduce 1 dose level.
	Mandatory: For Grade 4 thrombocytopenia associated with major bleeding, permanently discontinue study treatment.

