2.1.3.4 Date of last administration of study treatment

The date of last administration of the study treatment is defined as the last date when a non-zero dose of study treatment is administered and recorded on the “Study treatment” eCRF. This date will also be referred as last date of study treatment.

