2.9.1.2 AE analyses

Summary tables for AEs will include only the treatment-emergent events. AEs will be summarized by system organ class and/or preferred term, and severity (based on CTCAE version 5.0). Separate summaries will be provided for study treatment related treatment-emergent AEs, all deaths, on-treatment deaths, all serious adverse events and treatment-related SAEs, other significant AEs, treatment-related AEs leading to treatment discontinuation, dose adjustment, and additional therapy.

All AEs, deaths, and serious adverse events (including those from the pre- and post-treatment periods) will be listed and those collected during the post-treatment period will be flagged. A listing of AE MedDRA coding will be generated to provide the list of preferred terms that changed as a result of the re-mapping process to the latest MedDRA version.

A participant with multiple adverse events within a SOC will only be counted once towards the total of the system organ class. A participant with multiple occurrences of an AE will be counted only once in the respective AE category. A participant with multiple CTCAE grades for the same PT will be summarized under the maximum CTCAE grade recorded for the event. AEs with missing CTCAE grade will be included in the “All grades” column of the summary tables by grade and will be counted in both ‘missing grade’ and available maximum

grade in the summary tables by maximum grade. An AE with missing seriousness will be counted as non-serious AE.

In AE summaries, the SOC will be presented alphabetically, and the PT will be sorted within SOC in descending frequency. Summaries by CTCAE grade will present columns for grades 3/4, grade 5, and all grades, as applicable.

In summary, the following AE summaries will be generated:

- AEs regardless of study treatment relationship
- AEs suspected to be study treatment related
- On-treatment deaths, by SOC and preferred term
- All deaths, by SOC and preferred term
- SAEs regardless of study treatment relationship
- SAEs suspected to be study treatment related
- AEs leading to permanent discontinuation of study treatment regardless of study treatment relationship
- AEs leading to permanent discontinuation of study treatment suspected to be study treatment related
- AEs requiring dose adjustment and/or study treatment interruption regardless of study treatment relationship
- AEs requiring dose adjustment and/or study treatment interruption suspected to be study treatment related

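### A dose hold still open at the data cut-off is left out of the interruption summary and the RDI denominator; the effect is small and confined to descriptive tables

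*SAP*

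**What the plan says.** **Counting rule.** SAP 2.5.1.4: "An interruption is defined as a dose of zero given on one or more days between two non-zero dosing records". It then adds: "For participants who have dose interruption checked on the eCRF but never resume a non-zero dose, the dose interruption will not be counted". The length of an interruption is measured to the first dose taken after it, so it exists only where dosing restarted. The same section says: "Permanent discontinuations of study treatment will be summarized in the disposition table".

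**Disposition.** SAP 2.3.8 has a row for "Number (%) of participants who are still on-treatment". A participant with no end of treatment falls there. SAP 2.1.1 bars data from after the cut-off from every derivation, so a restart one day later cannot rescue the count.

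**Exposure and RDI.** SAP 2.1.3.4 takes as the last treatment date the "last date when a non-zero dose of study treatment is administered". SAP 2.5.1.1 uses that date as the end of exposure and says: "The duration includes periods of temporary interruption". SAP 2.5.1.3 divides cumulative dose by this duration and compares the result with a planned 400 mg/day. SAP 2.5.1 tabulates RDI in four bands with limits at 75%, 90% and 110%.

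**Related text.** Protocol 9.2.3 plans a summary of participants with dose adjustments, including interruptions, with reasons and with no resumption condition. SAP 4.1.1 Scenario 1 sets the last dosing date to the cut-off when a dose end date is wholly missing and there is neither end of treatment nor death; it is written for exceptional missing dates.

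**The concern.** The cut-off is planned while some participants are still receiving treatment, so some may be on hold that day. For them the counting rule removes the hold, the disposition table shows ordinary ongoing treatment, and the exposure clock has already stopped. The statement that duration includes temporary interruptions then works only for holds that were followed by another dose.

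What is at stake is the accuracy of the tolerability description: the number of participants interrupted, the length of interruptions, and RDI. The error has one direction. Leaving out an open hold can only lower the interruption count and raise RDI. It also departs from the SAP's general convention in 2.1.1, under which events that started by the cut-off and have no end date are reported as ongoing.

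**Working it through.** **Inputs.** The planned dose intensity is 400 mg/day (SAP 2.5.1.3), which reproduces as 2 x 200 mg. Scans fall every 6 weeks from first dose and continue through dose interruptions (Protocol 8.4.1). The primary cut-off requires at least 4 tumor assessments in participants still on treatment (Protocol section 9; SAP 2.1.1). Four scheduled scans put such a participant at about week 24, which is 24 x 7 = day 168, or day 161 at the early edge of the 7-day window. Protocol 6.5.1 generally requires discontinuation once a hold exceeds 21 days, with exceptions by approval.

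**Formulas.** Let D be days from first dose to cut-off and H the length of the open hold, with full dose on all other days.

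- SAP as written: cumulative dose = 400 x (D - H) and duration = D - H, so RDI = 100% for every H.
- Hold included: duration = D, so RDI = 100 x (D - H) / D.

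**Results at D = 168.**

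| Open hold (days) | RDI, SAP as written | RDI, hold included | RDI band, hold included |
|---|---|---|---|
| 7 | 100% | 161/168 = 95.8% | >90 to 110% (unchanged) |
| 14 | 100% | 154/168 = 91.7% | >90 to 110% (unchanged) |
| 21 | 100% | 147/168 = 87.5% | >75 to 90% |

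**Where the band changes.** RDI reaches 90% or below when H >= 0.10 x 168 = 16.8. A hold of 16 days gives 152/168 = 90.5%, and one of 17 days gives 151/168 = 89.9%. Reaching 75% or below would need H >= 0.25 x 168 = 42 days, twice the usual limit. At D = 161 a 21-day hold gives 140/161 = 87.0%. The effect shrinks with longer follow-up: a 21-day hold changes the band only if D <= 21/0.10 = 210 days.

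**The result turns on one dose.** Take 168 days containing 147 full-dose days and a 21-day hold.

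- 146 dosing days, the hold, then one dosing day on day 168: one interruption is counted and RDI = 147/168 = 87.5%.
- 147 dosing days, then the hold up to the cut-off: no interruption is counted and RDI = 147/147 = 100%.

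The total dose and elapsed time are the same in both cases.

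**The case against.** The strongest reply is that little is lost. An AE-driven hold can still appear under "AEs requiring dose adjustment and/or study treatment interruption regardless of study treatment relationship" (SAP 2.9.1.2), all doses are listed with reasons for change (SAP 2.5.1), and the tables concerned are descriptive. That limits the importance but does not close the gap. The AE table gives neither duration nor RDI, and it does not cover holds for other reasons, such as the one required during palliative radiotherapy (Protocol 6.8.1.3). A listing is not a summary. Scenario 1 in SAP 4.1.1 could bring an open hold into the denominator, but it addresses missing dates, and 2.1.3.4 still asks for a non-zero dose. Two programmers could therefore derive different RDIs.

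Three stronger readings are tempting, and the documents do not support them.

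- *The participants with the worst tolerability disappear.* Those who never restart because of toxicity are reported as discontinuations with their primary reason (SAP 2.3.8), and SAP 2.9.1.2 tabulates AEs leading to discontinuation. Leaving such a hold out of the interruption count is a reasonable way to avoid double counting.
- *RDI can be badly overstated.* With 42 days of dosing and a 20-day open hold, RDI would be 42/62 = 67.7% instead of 100%. That participant would be at day 62, but the primary cut-off requires about 24 weeks of follow-up for anyone still on treatment. The interim analyses have a separate plan.
- *The number affected can be estimated.* Protocol 2.2.3.3.2 gives treatment-related AE interruptions of 1/11 at 200 mg b.i.d. and 7/39 across doses, but 4 of those 7 were at 300 mg b.i.d. Nothing in the documents gives the share of holds that would be open at a cut-off.

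Nor is a difference between the AE table and the dosing table a fault in itself, because they count different things.

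**Conclusion.** The gap is real but narrow: it covers holds open at the cut-off in participants without end of treatment. Under the plain text they are uncounted as interruptions, have no duration, and do not lower RDI. The overstatement of RDI is about 4 to 12.5 percentage points for open holds of 7 to 21 days at about day 168, and less with longer follow-up. These figures assume one open hold, full dose otherwise, and a cut-off reached through four scheduled scans. Earlier reductions or interruptions would place a participant nearer a band limit, and an approved hold beyond 21 days would have a larger effect. ORR, DOR and the hypothesis tests are unaffected. The change is worth making because the rule always errs in the favourable direction and is easy to correct.

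**What to change.** Amend the SAP as follows.

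1. In 2.5.1.4, limit the exclusion sentence to interruptions that end in permanent discontinuation.
2. Count interruptions open at the cut-off in a separate row labelled ongoing at cut-off, with their duration censored at that date.
3. In 2.5.1.1 and 2.5.1.3, for participants on hold without end of treatment or death, end the exposure duration and the RDI denominator at the cut-off.
4. State how 2.1.3.4 and Scenario 1 of 4.1.1 fit together, so that a single rule governs an open zero-dose record.

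It is not necessary to count every zero-dose period up to end of treatment. That would label zero-dose days recorded just before any discontinuation, including one for progression, as an interruption and inflate the rate.

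The cost is SAP wording and minor programming, with no change to data collection or to any clinical rule. The reported interruption rate will be slightly higher and RDI slightly lower.
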